1. INTRODUCTION AND OBJECTIVES

The purpose of this study, in subjects with progressive measurable metastatic colorectal cancer (mCRC), is as follows:

- To evaluate the safety and tolerability of imalumab in combination with 5-fluorouracil (5-FU)/leucovorin (LV) or panitumumab to determine the recommended phase 2 dose (RP2D) of each combination
- To compare the efficacy of imalumab in combination with 5-FU/LV versus standard of care (SoC) (investigator choice) as third or fourth treatment line in subjects with KRAS mutated (mut) and/or NRAS mut tumors
- To compare the efficacy of imalumab in combination with panitumumab versus SoC (investigator choice) as third or fourth treatment line in subjects with KRAS wild type (wt) and NRAS wt tumors

Furthermore, the pharmacokinetic (PK) profile of imalumab in combination with 5-FU/LV or panitumumab will be characterized, and limited pharmacodynamic (PD) serum markers will be explored.

The statistical analysis plan outlines the methods for the planned final analysis in the protocol. As the study will continue to be on-going, an additional analysis addendum to the study report will be performed at the completion of the study.

1.1 Study Objectives

1.1.1 Primary Objectives

1. To determine the RP2D of imalumab in combination with 5-FU/LV or panitumumab (Part 1)
2. To compare progression-free survival (PFS) between imalumab in combination with 5-FU/LV for subjects with KRAS mut and/or NRAS mut tumors or in combination with panitumumab for subjects with KRAS wt and NRAS wt tumors, versus SoC (investigator choice) as third or fourth treatment line (Part 2)

1.1.2 Secondary Objective(s)

1.1.2.1 Efficacy

1. To compare overall response rate (ORR) and clinical benefit rate (CBR) in subjects treated at RP2D with imalumab in combination with 5-FU/LV or panitumumab versus SoC (investigator choice) as third or fourth treatment line

2. To compare overall survival (OS) of subjects who received imalumab in combination with 5-FU/LV or panitumumab versus SoC (investigator choice) as third or fourth treatment line

1.1.2.2 Safety

- To assess the safety and tolerability of imalumab in combination with 5-FU/LV or panitumumab.

1.1.2.3 Pharmacokinetics

- To characterize the PK of imalumab in combination with 5-FU/LV or panitumumab.

1.1.2.4 Health-related Quality of Life

- To compare health related quality of life (QoL) of subjects who received imalumab in combination with 5-FU/LV or panitumumab versus SoC (investigator choice) as third or fourth treatment line.

1.1.3 Exploratory Objectives

1.1.3.1 Pharmacodynamics

The exploratory PD objective of the study is to characterize oxidized macrophage migration inhibitory factor (oxMIF) and total MIF in plasma prior to and during treatment with imalumab in combination with 5-FU/LV or panitumumab.

1.1.3.2 Genetic Biomarkers

The exploratory genetic biomarker objective of the study is to characterize tumor-associated genetic alterations in blood/urine (for all subjects treated with imalumab in combination with 5-FU/LV or panitumumab who provide consent for exploratory biomarker analyses).

The sponsor will obtain available historical tumor mutational testing results for subjects.

1.1.3.3 Quality of Life

The exploratory QoL objective of the study is to compare disease-specific QoL and health utility in subjects treated with imalumab in combination with 5-FU/LV or panitumumab versus SoC (investigator choice) as third or fourth treatment line

2. STUDY DESIGN

This study is Phase 2a, randomized, open-label study to assess the safety, tolerability, and efficacy of imalumab in combination with 5-FU/LV or panitumumab versus Standard of Care (SOC) in subjects with metastatic colorectal cancer.

This study will be conducted in approximately 40 study sites in the United States (US) and the European Union (EU). The study will comprise 2 sequential parts (subjects can only participate in either Part 1 or Part 2 of the study):

- Part 1: A Safety Run-in period to evaluate 2 predefined doses (7.5 mg/kg and 10 mg/kg) of imalumab given every week (QW) in combination with infusional 5-FU/LV given every 2 weeks (Q2W) in subjects with mutated tumors (KRAS mut, NRAS mut), or imalumab in combination with panitumumab given Q2W in subjects with wild type tumors (KRAS wt and NRAS wt). Prior to entry into the study, subjects will be stratified according to their KRAS/NRAS mutation status. Treatments will be administered in 4-week (28-day) cycles.
- Part 2: A 2-treatment-arm design using a 2:1 ratio for subjects to receive imalumab + 5-FU/LV or imalumab + panitumumab (Arm A) or SoC per investigator choice (Arm B). Prior to randomization, subjects will be stratified according to their mutation status. Within each stratum, subjects will be randomized in a 2:1 ratio to receive imalumab + 5-FU/LV (KRAS mut, NRAS mut tumors) or imalumab + panitumumab (KRAS wt and NRAS wt tumors) (Arm A) or SoC per investigator choice (Arm B).

For all subjects in Parts 1 and 2, treatment will continue until disease progression, unacceptable toxicity, or withdrawal of consent.

Part 1: Safety Run-in

For each combination, subjects will be enrolled into 2 sequential cohorts, with a minimum of 3 and a maximum of 6 subjects per cohort.

For each combination, enrollment will proceed according to the following rules based on the occurrence of dose-limiting toxicities (DLTs):

- If zero out of 3 evaluable subjects experience a DLT during the first 28 days after the first administration of study drug at the first dose level, the second dose level

will be opened for enrollment after review of the safety data by the Data Review Committee (DRC).

- If 1 out of 3 evaluable subjects experiences a DLT during the first 28 days after administration of study drug at the first dose level, 3 additional subjects will be enrolled at the first dose level, for a total of 6 evaluable subjects. After review of the safety data of all 6 evaluable subjects, the DRC will decide if the second dose level or a lower dose level will be explored.
- If 2 or more evaluable subjects experience a DLT during the first 28 days after the first administration of study drug at the first dose level, the second dose level will not be open to enrollment and the DRC will decide if a lower dose level will be explored.

The DRC will meet for safety reviews after 3 subjects in a dosing cohort have completed the first treatment cycle. The DRC will decide either to enroll additional subjects or open the next dose level. For each combination, based on all data of all evaluable subjects, the DRC will either determine the RP2D, or will decide to explore an intermediate dose level.

DLT Definition

A DLT is defined as any drug-related treatment-emergent adverse event (TEAE) (graded according to the National Cancer Institute Common Terminology Criteria for Adverse Events [NCI CTCAE] v4.03) that occurs during the first 28 days after treatment start and that meets any of the following criteria:

- Any \geq Grade 3 non-hematologic toxicity excluding:
 - Mucositis/stomatitis of Grade 3 that resolves to Grade 1 or less with supportive measures within 7 days
 - Diarrhea of < 3 days duration following adequate and optimal therapy
 - Nausea and vomiting of < 3 days duration with adequate and optimal therapy
 - Fatigue of < 7 days duration following initiation of adequate supportive care
 - Alopecia
 - Any single laboratory value out of the normal range that has no clinical significance and that resolves to \leq Grade 2 with adequate measures within

7 days; transient Grade 3 elevations (lasting < 5 days) of hepatic transaminases in the absence of simultaneous increase in serum bilirubin

- Any Grade 4 hematologic toxicity excluding:
 - Grade 4 neutropenia lasting for \leq 5 days and not accompanied by fever
 - Isolated Grade 4 lymphocytopenia without clinical correlate
- Grade 3 febrile neutropenia
- Grade 3 thrombocytopenia associated with bleeding
- Any life-threatening complication or abnormality not covered in the NCI CTCAE v4.03

Determination of RP2D

For each combination, based on all data of all evaluable subjects, the DRC will determine the RP2D, or decide if an intermediate dose level must be explored.

Part 2: Exploratory Phase 2a

This is a 2-treatment-arm study in which subjects will receive imalumab + 5-FU/LV or imalumab + panitumumab (Arm A) or SoC per investigator choice (Arm B). Prior to randomization, subjects will be stratified according to their KRAS/NRAS status. Within each stratum, subjects will be randomized in a 2:1 ratio to receive imalumab + 5-FU/LV (KRAS mut and/or NRAS mut tumors) or imalumab + panitumumab (KRAS wt and NRAS wt tumors) (Arm A) or SoC per investigator choice (Arm B). Randomization will occur via an Interactive Response Technology (IRT) System. For each combination in Arm A, subjects will receive imalumab at the RP2D determined in Part 1 for the corresponding combination. All subjects will be treated until disease progression, unacceptable toxicity, or withdrawal of consent.

An independent Data Safety Monitoring Board (DSMB), comprised of recognized experts in the field of oncology, biostatistics, clinical care and research will review accumulating safety data. The composition, activities, and responsibilities of the DSMB are described in further detail in the DSMB Charter.

2.1 Study Population

Male and female subjects aged 18 years or older with a confirmed diagnosis of mCRC are eligible if they have progressed after receiving at least 2, but no more than 3, prior treatment lines including SoC, and have an Eastern Cooperative Oncology Group (ECOG) Performance Status (PS) of 0-2.

2.2 Inclusion and Exclusion Criteria

2.2.1 Inclusion Criteria

Subjects who meet ALL of the following criteria are eligible for this study:

1. Provision of a signed informed consent
2. Male and female subjects 18 years of age and older at the time of screening
3. Subjects who progressed after receiving at least 2, but no more than 3, prior cancer drug therapy treatment lines including SoC in the metastatic setting
4. Anticipated life expectancy >3 months at the time of screening
5. Weight between 40 kg and 180 kg
6. Histologically or cytologically confirmed diagnosis of CRC
7. Metastatic CRC not amenable to surgical resection
8. Known KRAS, NRAS mutation status (if unknown status for either of these genes and no archival tissue is available, a fresh tumor biopsy will be obtained)
9. At least 1 measurable lesion as defined by RECIST v1.1
10. Eastern Cooperative Oncology Group (ECOG) Performance Status (PS) of 0-2
11. Adequate hematological function, defined as:
 - a. Platelet count $\geq 100,000/\mu\text{L}$
 - b. Prothrombin time and activated partial thromboplastin time (aPTT) < 1.5 times the upper limit of normal (ULN)
 - c. Absolute neutrophil count (ANC) $\geq 1,000/\mu\text{L}$
 - d. Hemoglobin $\geq 9 \text{ g/dL}$, without the need for transfusion in the 2 weeks prior to screening
12. Adequate renal function, defined as serum creatinine ≤ 2.0 times ULN and creatinine clearance $> 50 \text{ mL/min}$ or estimated glomerular filtration rate $> 50 \text{ mL/min}/1.73 \text{ m}^2$
13. Adequate liver function, defined as:
 - a. Aspartate aminotransferase (AST) and alanine aminotransferase (ALT) ≤ 2.5 times ULN for subjects without liver metastases, or ≤ 5 times ULN in the presence of liver metastases
 - b. Bilirubin ≤ 2.0 times ULN, unless subject has known Gilbert's syndrome
14. Adequate venous access
15. For female subjects of childbearing potential, the subject presents with a negative serum pregnancy test at screening and agrees to employ 2 forms of adequate birth control methods, including at least 1 barrier method (eg, diaphragm with spermicidal jelly or foam, or [for male partner] condom) throughout the course of the study and for at least 90 days after the last administration of imalumab. In

addition, these birth control methods must be continued for at least 180 days after last administration of 5-FU in subjects who receive this treatment. Secondary contraceptive measures could be either birth control pills, patches, or intrauterine devices.

16. For male subjects, they must agree to use adequate contraceptive measures including at least 1 barrier method (eg, condom with spermicidal jelly or foam and [for the female partner] diaphragm with spermicidal jelly or foam, birth control pills/patches, or intrauterine device) and abstain from sperm donation throughout the course of the study and for at least 90 days after the last administration of imalumab. In addition, these birth control methods must be continued for at least 180 days after last administration of 5-FU in subjects who receive this treatment.
17. Subject is willing and able to comply with the requirements of the protocol

2.2.2 Exclusion Criteria

Subjects who meet ANY of the following criteria are not eligible for this study:

1. Known central nervous system metastases
2. Prior malignancy(s) within the past 3 years, with the exception of curatively treated basal or squamous cell carcinoma of the skin, locally advanced prostate cancer, ductal carcinoma in situ of breast, in situ cervical carcinoma and superficial bladder cancer
3. Prior treatment with panitumumab for subjects with KRAS wt and NRAS wt tumors
4. Known history of keratitis, ulcerative keratitis, or severe dry eye in subjects with KRAS wt and NRAS wt tumors
5. Residual adverse event (AE) from previous treatment > Grade 1, except neuropathy and alopecia
6. Prior intolerance to fluoropyrimidine for subjects with KRAS mut and/or NRAS mut tumors
7. Myocardial infarction within 6 months prior to Cycle 1 Day 1 (C1D1), and/or prior diagnoses of congestive heart failure (New York Heart Association Class III or IV), unstable angina, unstable cardiac arrhythmia requiring medication; and/or the subject is at risk for polymorphic ventricular tachycardia (eg, hypokalemia, family history, or long QT syndrome)
8. Uncontrolled hypertension, defined as systolic blood pressure ≥ 160 mmHg and/or diastolic blood pressure ≥ 100 mmHg confirmed upon repeated measures

9. Left ventricular ejection fraction (LVEF) < 40% as determined by echocardiogram(ECHO)/multigated acquisition scan (MUGA) performed at screening or within 90 days prior to C1D1
10. QT/QTc interval > 450 msec, as determined by screening ECG performed no earlier than 1 week before C1D1
11. Prior anti-tumor therapy (chemotherapy, radiotherapy, antibody therapy, molecular targeted therapy, retinoid therapy, or hormonal therapy) within 4 weeks (< 28 days) prior to C1D1
12. Major surgery within 4 weeks (< 28 days) prior to C1D1
13. Active joint inflammation or history of inflammatory arthritis or other immune disorder involving joints (osteoarthritis is not exclusionary)
14. Active infection involving IV antibiotics within 2 weeks prior to C1D1
15. Known history of or active hepatitis B virus (HBV) and/or hepatitis C virus (HCV), or active tuberculosis
16. Known history of human immunodeficiency virus (HIV) type 1/2 or other immunodeficiency disease
17. Subject has received a live vaccine within 4 weeks (< 28 days) prior to C1D1
18. Known hypersensitivity to any component of recombinant protein production by CHO cells
19. Exposure to an investigational product or investigational device in another clinical study within 4 weeks (< 28 days) prior to C1D1, or is scheduled to participate in another clinical study involving an investigational product or device during the course of this study
20. Subject is breastfeeding or intends to begin breastfeeding during the course of the study
21. Any disorder or disease, or clinically significant abnormality on laboratory or other clinical test(s) (eg, blood tests, ECG), that in medical judgment of the investigator may impede the subject's participation in the study, pose increased risk to the subject, and/or confound the results of the study
22. Subject is a family member or employee of the investigator

2.3 Sample Size and Power Calculations

The final sample size of Part 1 (Safety Run-in) is dependent on the pre-stated rules for dose escalation. In Part 1, the sample size for each dosing regimen (ie, imalumab + 5-FU/LV and imalumab + panitumumab) is expected to be between 6 and 12 subjects (ie, 3 to 6 subjects at each 7.5 mg/kg and 10 mg/kg imalumab dose level). Non-evaluable subjects will be replaced to meet study objectives.

The sample size of Part 2 (Exploratory Phase 2a) is estimated to be a total of 66 subjects. Assuming that the median PFS is 2.4 months in the control arm and 4.25 months in the experimental arm (a constant hazard ratio 0.565), and using a one-sided log-rank test with α of 0.15 and β of 0.20 with a drop-out rate of 20% at 6 months, 48 PFS events are needed. With an enrollment ratio of 2:1, and taking into account the time for accrual of 1 year and an additional follow-up period of 6 months after the last subject is enrolled, the sample size needed is approximately 22 subjects in each of the 2 imalumab-containing treatment arms (imalumab + panitumumab and imalumab + 5-FU/LV) and in the control arm (SoC).

2.4 Randomization

There is no randomization in Part 1. In Part 2, randomization in permuted blocks will occur to minimize bias and fulfill a 2:1 ratio between Arm A and Arm B. Prior to randomization, subjects will be stratified according to their KRAS and NRAS mutation status. Randomization will occur via an IRT System until the targeted number of subjects in each treatment-arm is achieved.

2.5 Blinding/Unblinding

This is an open-label study.

2.6 Study Stopping Rules

This study will be stopped if 1 or more of the following criteria are met:

- Excessive toxicity or clinically meaningful SAE that may pose significant health risks
- Decision by the sponsor to interrupt or terminate the study at any time for reasons including, but not limited to, safety or ethical issues or insufficient compliance

When feasible, the sponsor will provide advance notification to the investigator of the impending action prior to its taking effect. The sponsor will promptly inform all other investigators and/or institutions conducting the study if the study is interrupted or terminated for safety reasons, and will also inform the regulatory authorities of the interruption or termination of the study and the reason(s) for the action. If required by applicable regulations, the investigator must inform the independent ethics committee/institutional review board (IEC/IRB) promptly and provide the reason for the interruption or termination.

Study completion is estimated to occur when 75% of OS events have been reported.

There are no specific statistical stopping rules defined for this study.

2.7 Study Assessments

A schedule of assessments is provided in Section [16.1](#).

2.8 Data Monitoring Committee

The composition, activities, and responsibilities of the DSMB are described in further detail in the DSMB Charter.

3. STUDY OUTCOME MEASURES

3.1 Efficacy Outcome Measures

3.1.1 Primary Efficacy Outcome Measure

The primary efficacy outcome measure is PFS defined as time between treatment initiation and tumor progression (per RECIST v1.1 criteria) or death from any cause, with censoring of subjects who are lost to follow-up or withdraw consent.

3.1.2 Secondary Efficacy Outcome Measures

The secondary outcome measures are:

- Response evaluation according to RECIST v1.1.
- OS, defined as time from randomization to death of any cause.

3.2 Safety Outcome Measures

3.2.1 Primary Safety Outcome Measures

The primary safety outcome measure is the occurrence of DLTs (Part 1).

3.2.2 Secondary Safety Outcome Measures

- Occurrence of serious adverse events (SAEs) and/or TEAEs, regardless of causality or relationship to study drug and coded according to NCI CTCAE v4.03
- Other safety measurements: physical or instrumental examinations, electrocardiograms (ECGs), vital signs, and clinically relevant changes in instrumental examinations or laboratory values

3.3 Immunogenicity Outcome Measures

- Occurrence of binding and/or neutralizing anti-imalumab antibodies

- Incidence and severity of infusion reactions after imalumab

3.4 Pharmacokinetic Outcome Measures

The PK outcome measure is the plasma concentrations of imalumab. Imalumab plasma PK will be characterized using a population PK modeling approach, in combination with data from other studies. The population PK modeling approach will be described and reported in separate documents.

3.5 Quality of Life Outcome Measures

The QoL outcome measures are derived from answers to the EORTC QLQ-C30 questionnaire.

3.6 Exploratory Outcome Measures

The exploratory PD outcome measures include plasma levels of oxidized macrophage migration inhibitory factor (oxMIF) and total MIF.

Genetic biomarkers will also be investigated as an optional exploratory outcome. Exploratory genetic biomarker outcome measures include tumor-associated genetic alterations of cfDNA in blood/urine, for subjects treated with imalumab in combination with 5-FU/LV or panitumumab who provide consent for these analyses. The sponsor will obtain available historical tumor mutational testing results for subjects.

The exploratory QoL outcome measures use the EORTC QLQ for colorectal cancer 29 (EORTC QLQ-CR29) and the European Quality of Life – 5 Dimensions questionnaire (EQ-5D). The EORTC QLQ-CR29 will be used as a supplement to the EORTC QLQ-C30 to assess the disease-specific aspects of colorectal cancer. The EQ-5D is a health utility measure.

4. ANALYSIS SETS

4.1 Full Analysis Set

The Full Analysis Set (FAS) will serve as the population for the analyses of efficacy data in the trial. The FAS will include all subjects who 1) received at least 1 administration of study drug, and 2) have 1 post-baseline tumor response assessment based on RECIST v1.1, or died within 18 weeks of the start of treatment.

The proposed derivation of PFS (Section 7.1.1) indicates that subjects who miss 2 planned tumor assessments will be censored at the last tumor assessment before the

missed assessments. For this study, the exact time period that identifies that 2 tumor assessments have been missed will be defined as twice the protocol-defined time between scans (8 weeks) + the protocol allowed visit window (1 week) (ie, $2 * 8 + 1 = 18$ weeks).

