13.2 Datasets and Analysis Cohorts

The Safety Population is defined as all subjects who receive at least 1 administration of IP. The Safety Population will be used for all safety analyses in the trial.

The Full Analysis Set (FAS) will serve as the population for the analyses of efficacy data in the trial. The FAS will include all subjects who 1) received at least 1 administration of IP, and 2) have 1 post-baseline tumor response assessment based on RECIST v1.1 or died within 18 weeks of the start of treatment.

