4.2 Safety Analysis Set

The Safety Analysis Set is defined as all subjects who receive at least 1 administration of study drug. The Safety Population will be used for all safety analyses in the trial.

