5.3 Definition of Baseline

Baseline will be defined as the last assessment before the date and time of first administration (C1D1) of imalumab or SoC. For subjects who have not received any study drug, the baseline will be the last assessment performed at Screening, Baseline, or C1D1.

If more than one baseline scan is recorded then measurements from the one that is closest and prior to the date of randomization will be used to define the baseline.

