This will be regardless of whether the subject receives another anti-cancer therapy prior to progression. Subjects who have not progressed or died at the time of analysis will be censored at the time of the latest date of assessment from their last evaluable RECIST assessment. However, if the subject progresses or dies after two or more missed tumor assessments, the subject will be censored at the time of the latest evaluable RECIST assessment. If the subject has no evaluable visits or does not have baseline data they will be censored at 1 day unless they die within two visits of baseline. For this study, the exact time period that identifies that two tumor assessments have been missed will be defined as twice the protocol-defined time between scans + the protocol allowed visit window. RECIST assessments are scheduled to occur every other cycle, ie, every 8 weeks \pm 1 week. If tumor scans indicate progression or the subject dies more than $2*9$ weeks=18 weeks (126 days) after the previous tumor assessment, the subject will be censored on the date of the assessment prior to progression or death.

Table 2 below specifies the date of disease progression or censoring rules that will be carried out for the PFS analysis:

Table 2: Date of Progression or Censoring for Progression-free Survival

Situation	Date of Disease Progression or Censoring	Outcome
Alive with no post-baseline assessments for tumor response	Treatment start date	Censored
Disease progression or death after two or more consecutive missed tumor response assessments	Date of last scan for tumor assessment showing no evidence of disease progression that is before the first missed visit.	Censored
Not known to have progressed or died according to data in the database as of data-cut-off	Date of last scan for tumor assessment showing no evidence of disease progression	Censored
Withdrawal from the study or loss to follow-up	Date of last scan for tumor assessment prior to withdrawal or loss to follow-up	Censored
Disease progression reported on multiple response assessments	Earliest Date of Progression as defined in this Section	Progressed
Death without Disease Progression	Date of death	Progressed

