7.3 Sensitivity Analyses

A sensitivity analysis will be conducted for PFS. The calculation of PFS will be the same as described in Section 7.1.1 except that subjects will also be censored at the latest tumor assessment prior to the start of a new anti-cancer therapy.

If any subjects are censored because they missed 2 tumor assessments, a second sensitivity analysis will be conducted to include these subjects as events. Otherwise, the calculation of PFS will be the same as described in Section 7.1.1.

A third sensitivity analysis will include subjects in Part 1 cohorts and be summarized by integrated treatment group.

The same statistical analysis methods used for the primary analysis of PFS, ie, log-rank test and Cox regression, will be used for all of these sensitivity analyses.

The best % change from baseline in target tumor diameters will be presented for each subject in a waterfall plot by study cohort.

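### The only efficacy set depends on dosing and on a later scan or early death, and no all-randomised analysis is planned; primary PFS is almost untouched, but OS, ORR and CBR are not

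*SAP*

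**What the plan says.** SAP 4.1 makes the FAS the population for efficacy: "The FAS will include all subjects who 1) received at least 1 administration of study drug, and 2) have 1 post-baseline tumor response assessment". Death within 18 weeks of treatment start is accepted in place of the scan. Protocol 13.2 has the same structure but a different drug term: "The FAS will include all subjects who 1) received at least 1 administration of IP".

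The only other set also requires dosing: "The Safety Analysis Set is defined as all subjects who receive at least 1 administration of study drug" (SAP 4.2). ORR and CBR use the FAS count as denominator (SAP 7.2.1.2), and OS follows the PFS methods (SAP 7.2.1.1).

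SAP 7.3 plans three PFS sensitivity analyses. The first censors at new anti-cancer therapy. The second turns subjects censored for two missed assessments into events. The last is this: "A third sensitivity analysis will include subjects in Part 1 cohorts and be summarized by integrated treatment group". None uses all randomised subjects.

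Other sections write rules for people the FAS leaves out:

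- SAP 5.3: "For subjects who have not received any study drug, the baseline will be the last assessment performed at Screening, Baseline, or C1D1".
- SAP 7.1.1, Table 2, first row, covers subjects "Alive with no post-baseline assessments for tumor response" and censors them at treatment start.
- The text of SAP 7.1.1 says of subjects with no evaluable visit that "they will be censored at 1 day unless they die within two visits of baseline".

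SAP 5.5 moves the start of PFS to randomisation, to match OS, but the analysis set stays tied to dosing.

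**The concern.** Randomisation protects a comparison only while membership is fixed at randomisation. Here it is not. Take two dosed subjects with no post-baseline scan: the one who dies in week 10 is kept, and the one who is still alive after week 18 is dropped, along with any survival data collected later. A subject randomised but never dosed is in no analysis set at all.

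The trial is open-label, so whether a subject returns for a scan could differ by arm. Only an all-randomised analysis is immune to that. At stake are OS, ORR and CBR, one PFS sensitivity analysis and, through the dosing condition only, primary PFS.

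**Working it through.** **1. The plan's own figure.** Inputs (SAP 2.3): hazard ratio 0.565, one-sided alpha 0.15, power 80%, 2:1 allocation. Schoenfeld: (1.036 + 0.842)² / [(2/3)(1/3)(ln 0.565)²] = 48.7 events, against 48 stated; 48 events give 79.6% power. The sizing reproduces and is not in question.

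**2. Scan condition and primary PFS.** A dosed subject outside the FAS cannot have a countable event. Progression needs a scan. Death within 18 weeks puts the subject in the FAS. A later death follows two missed assessments and is censored. Such a subject would be censored at day 1 and add almost nothing to the log-rank test. In 1,500 simulated trials with the plan's assumptions (about 3 of 66 excluded on average, at most 10), the statistic was identical in every run with censoring at time zero. With censoring at one day it was identical in 84%, since an event in the first day can then fall in the shared risk set; the average hazard ratio was 0.565 either way.

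**3. Dosing condition and primary PFS.** An undosed subject who dies early is lost as an event. Such subjects should be few, because randomisation takes place at the Cycle 1 Day 1 predose visit (Protocol 10.3.2).

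**4. Second PFS sensitivity analysis.** An unscanned death after 18 weeks would count here if the subject were not excluded. The same simulation gave 54.5 events in all randomised against 53.0 in the FAS, with the log-rank statistic identical in only 23% of runs.

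**5. How many are dropped.** Drop-out of 20% at 6 months (SAP 2.3), taken as exponential: rate = −ln(0.8)/6 per month; by week 8, 1 − exp(−rate × 56/30.44) = 6.6%. That is 2.9 of 44, 1.5 of 22 and 4.4 of 66. Exit scans (Protocol 10.3.3.8 and 10.3.3.9) lower this: if 50% or 75% of early leavers attend one (assumed), 2.2 or 1.1 of 66 stay unscanned. Withdrawals for toxicity or clinical progression (Protocol 9.3) are not counted and would raise it.

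**6. ORR and CBR.** Dropped subjects are non-responders, so each rate can only rise. With equal 6.6% loss both are multiplied by 1/(1 − 0.066) = 1.07; an assumed CBR of 50% v 35% becomes 53.5% v 37.5%, difference 15.0 to 16.1 points. With an assumed CBR of 50.0% in both arms (22/44 and 11/22):

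| Dropped, A and B | Arm A | Arm B | Difference |
|---|---|---|---|
| 3 and 1 | 22/41 = 53.7% | 11/21 = 52.4% | +1.3 |
| 3 and 2 | 22/41 = 53.7% | 11/20 = 55.0% | −1.3 |
| 1 and 3 | 22/43 = 51.2% | 11/19 = 57.9% | −6.7 |

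The standard error of the difference is √(0.25/44 + 0.25/22) = 13.1 points.

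**7. OS.** True hazard ratio 1.0, exponential survival with assumed medians of 5 to 9 months, 12 months' accrual plus 6 months' follow-up, 2,000,000 simulated subjects per setting. FAS hazard ratio by assumed unscanned share:

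| Arm A v Arm B | Lost to survival follow-up | Kept in survival calls |
|---|---|---|
| 6.6% v 6.6% | 1.00 | 1.00 |
| 5% v 10% | 0.99 | 0.98 |
| 10% v 5% | 1.01 | 1.02 |
| 3.3% v 13.2% | 0.98–0.99 | 0.96 |
| 13.2% v 3.3% | 1.01–1.02 | 1.05 |

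The all-randomised hazard ratio was 0.998 to 1.003 throughout. Expected deaths are 52 to 39, so the standard error of the log hazard ratio, 1/√(deaths × 2/9), is 0.29 to 0.34. Within an arm, where dropped subjects stay in the survival calls, OS is pulled down: in a separate run with assumed medians of 8 and 6 months, simulated medians went from 8.1 to 7.9 and from 6.25 to 6.0. The arm that loses more therefore looks worse on OS and better on ORR and CBR. Nothing in the documents says which arm that will be.

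**The case against.** The strongest case is that this is close to a preference. The trial is an exploratory Phase 2a with one-sided alpha 0.15, SAP 5 calls the secondary endpoints supportive, and every shift in the tables is well inside one standard error. The death clause already keeps unscanned early deaths. Protocol 13.4.2 and SAP 6.1 will report who was randomised but untreated and how many are in each set. This stands as an argument for low severity. It does not answer the point itself: counting exclusions does not analyse them.

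In the other direction, small is conditional and not shown, because it rests on assumed losses. More lopsided losses do more: with an assumed CBR of 22/44 v 8/22, dropping six from Arm B alone moves the difference from 13.6 points to 0.0. Nothing in the documents points to such a loss.

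A reader might infer that the dosing condition removes Arm B subjects on best supportive care, or, taking IP literally as imalumab, the whole control arm. The documents do not support that. SAP 5.3 dates baseline from "first administration (C1D1) of imalumab or SoC", and Protocol Table 4 gives best-supportive-care subjects a full schedule with tumour measurements. Were such subjects excluded (assumed 20% of Arm B at twice the hazard of other controls), the PFS hazard ratio would go from 0.488 to 0.548. That is reason to settle the wording, but it is an ambiguity and not a shown exclusion.

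**Conclusion.** The point holds as a definitional weakness of modest size. Membership of the only efficacy set depends on events after randomisation, and no planned analysis covers everyone randomised. A reader might also infer that this biases primary PFS or favours imalumab. Neither is supported: the scan condition leaves primary PFS as it is, the dosing condition should touch few subjects, and the between-arm direction for OS, ORR and CBR is unknown.

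With equal loss at the planned drop-out rate the between-arm effect is small. The limits of about 5% on the OS hazard ratio and about 7 points on the CBR difference rest on assumed unequal losses, survival medians and response rates. Confidence is high on what the text says and lower on the size. Severity is at the low end of what should be fixed; the case for change is that it costs little.

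**What to change.** - In SAP 4.1 and Protocol 13.2, analyse PFS, OS, ORR and CBR in all subjects randomised in Part 2, by assigned arm. Keep the present FAS as a sensitivity set.
- Count unscanned subjects as not evaluable, hence non-responders, using the category already in SAP 7.2.1.2.
- In Table 2, first row, replace the treatment start date with day 1 from randomisation. This matches the text of SAP 7.1.1 and the new PFS origin, and an undosed subject has no treatment start date. For undosed subjects, start the 18-week early-death window at randomisation.
- Reconcile the derivation of that window: SAP 4.1 writes 2 × 8 + 1 as 18, though it is 17, while SAP 7.1.1 uses 2 × 9 = 18.
- For OS, censor undosed subjects at the last date known alive (SAP 7.2.1.1). Extend the 3-monthly survival calls to them, since Protocol 10.3.3.10 names only subjects who have stopped study drug or progressed.
- Reconcile IP with study drug, and state that Arm B subjects on best supportive care are in the efficacy set.

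Cost: document wording, survival calls for a few undosed subjects, one extra run of the efficacy tables, and slightly lower ORR and CBR.
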